The PS model will be developed, after all subjects have been enrolled, by an outcome-blinded independent party which will only have access to baseline characteristics and sterilization group. Balance of the PS baseline characteristics will be assessed at the 3-year interim analysis and end of study; if necessary, the process will be reevaluated to ensure balance of baseline characteristics throughout the study. The first interim analysis will be initiated after the PS matching process has completed. All 3 interim analyses will be performed on a PS-matched population in order to adjust for measured confounding as well as on the total population. In other words, the main analysis sets are the Adjusted Full Analysis Set (PS-matched population among subjects where a sterilization procedure of choice was

attempted) and the Full Analysis Set (sterilization procedure of choice was attempted) for the interim analyses. A Reliance Set will consider women relying on the sterilization method selected at the index event.

For all the outcomes and variables, a descriptive analysis will be performed and no statistical comparison will be made. For continuous data, N, mean, standard deviation, min, and max will be provided and for categorical data, frequency and percentages will be provided. Unless otherwise specified, the analyses will be presented in a way that events will be assigned to the treatment which was given initially at the index event.

Summaries for the interim analyses will use all data up to the data cutoff dates, which will be at the time enrollment ends, after all subjects complete 1 year of follow-up, and at the end of 3 years of follow-up. Serology data (cytokines, nickel and titanium levels, and nickel LPT results) will be summarized in the interim analysis to be performed at the end of 3 years of follow-up. The interim analysis report will also include a description of the pathologic and histologic findings of fallopian tubes, and individual dossiers provided to the Adjudication Committee in cases of potential hypersensitivity/allergy/autoimmune reactions.

Results of each interim analysis will be summarized in a separate report.

The interim analysis reports will be submitted no later than 3 months after database lock for each interim analysis data cutoff date.

11. Interim and final post market surveillance report

Section added by Amendment 2 (Modification 26). Section modified by Amendment 4 (Modification 1)

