#### **4.4.5 Main outcome events**

Incomplete start dates of outcome events for the time to event analyses will be imputed as follows:

- In case that only the day is missing, the date will be imputed as the first day of the month.
- In case that the day and the month are missing (i.e. only the year is available) the day and month will be imputed as January 1.
- In case the event start date is missing completely, index event date will be used as start date.
- If the imputed start date is before the index date, it will set to the index date.

Incomplete stop dates of outcome events for the time to event analyses will be imputed as follows:

- In case that only the day is missing, it will be imputed with last day of the month;
- In case that the day and the month are missing (i.e., only the year is available) it will be imputed as December 31.
- If the imputed dates are after the last date of contact, it will be set to the last date of contact.
- If the stop dates are completely missing, the event will be considered as ongoing at the time of end of study.

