## 6.4 Outcome endpoints and variables

The main objective of this observational study is to evaluate under routine clinical practice conditions the incidence of important treatment-emergent AEs under hysteroscopic sterilization (Essure) and laparoscopic tubal sterilization. An AE is considered as treatment-emergent when it starts or worsens on or after the index date and up to the date of subject withdrawal or the censoring date, as described in Sections 4.3 and 6.1.3.

The outcome endpoint and variables are presented in Table 2. The descriptive analysis will be performed for all the variables listed below and the comparative analysis will be performed only for the main endpoints.

For the main endpoints, the subject incidence (regardless of the time each subject is “at risk”) is the number of subjects with treatment-emergent events divided by the number of subjects at risk.

Laboratory evaluation results will be compared to their normal ranges. Any values out of normal ranges will be identified. The change from baseline for each laboratory parameter will also be presented for each post-baseline visit.

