Adverse Events	Any AE, Serious AEs, reason for serious AE, AE of special safety interest, AE intensity, AE related to study procedures or devices, type of procedure/device related to AE, AE outcome, pre-existing condition, concomitant medication, other non-study procedures
Contraceptive Method Post-procedure	Method used for contraception, duration of the contraceptive method used.
Concomitant Medication	Type of medication, main indication for medication
Additional Abdominal or Pelvic Surgery	Type of surgery performed, was surgery done for the purpose of sterilization/ re-sterilization , surgery due to an AE
Allergy/Hypersensitivity Evaluation, Autoimmune Disorder Evaluation, and PRO Alert Response	Symptom subjects reported, adjudication committee form, pathological findings, serum or plasma nickel and titanium levels, NiLPT and chromium LPT results, cytokine samples analysis , type of alert, pain alert response and bleeding response.
Study Completion	Did subject complete study, primary reason for premature discontinuation, time to premature discontinuation
Death	Number subjects died

a Only measured for Essure Group

b Only measured for laparoscopic tubal sterilization group

For the main outcomes, [Table 3](#) lists the SMQ search terms for abnormal uterine bleeding and lower abdominal and/or pelvic pain. Per the definition by the American College of Obstetricians and Gynecologists, chronic pelvic pain is pain in the pelvic area that lasts for 6 months or longer (i.e., the stop date of the pain minus start date is longer than 182 days, or by the time of EOS, the subject still has pain ongoing with start date 182 days before EOS).

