#### **6.4.2 Exposure-adjusted subject incidence**

The exposure-adjusted subject incidence is defined as the number of subjects with at least one event divided by the total time at risk. For the subject who has at least one event, the risk duration is from the index date to the date of the first event. For the subject who has no events reported, the risk duration is from the index date to the censoring date or end of study date. The exposure adjusted incidence will be calculated for each group. The difference between two groups and its associated 95% CI will be calculated using the method proposed by Liu et.al (2006) [1].

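### Chronic pain needs 182 observed days after onset, but risk time runs to the end of follow-up, so absolute chronic-pain rates read low and are not comparable between the interims and the final analysis

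*SAP*

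**What the plan says.** The definition stands in SAP 6.4, in the paragraph after Table 2. Resolved pain is chronic if "the stop date of the pain minus start date is longer than 182 days". Unresolved pain is chronic if "by the time of EOS, the subject still has pain ongoing with start date 182 days before EOS".

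The SAP does not name the event date for this endpoint. Onset is the natural reading, because the surrounding rules work from start dates:

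- SAP 6.4: "An AE is considered as treatment-emergent when it starts or worsens on or after the index date".
- SAP 4.4.5: "Incomplete start dates of outcome events for the time to event analyses will be imputed as follows". That section goes on to impute start dates.

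Risk time is set in SAP 6.4.2. For a woman with an event, "the risk duration is from the index date to the date of the first event". For a woman without one, "the risk duration is from the index date to the censoring date or end of study date". SAP 6.4.1 divides by all subjects at risk and requires no minimum observation. SAP 6.4.3 right-censors at the end of observation. None of these sections makes an exception for chronic pain. The sensitivity analysis in SAP 6.8 ignores censoring events but still runs to the end of study.

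Two further provisions matter. SAP 4.3 says data collection continues for all subjects until end of study or early termination, so women censored for analysis are still observed. For the interims, Protocol 10.5 says: "Summaries for the interim analyses will use all data up to the data cutoff dates". Neither document says what replaces EOS at a cutoff, or what EOS means for a woman who drops out.

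**The concern.** Whether an onset counts as an event depends on at least 182 days of observation after it, but the denominator makes no allowance for that. A woman whose pain starts 100 days before she leaves the study, or before a data cutoff, is scored as event-free and contributes all her time. The shorter the follow-up, the larger the share of time in which nothing can be scored.

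Chronic pain is the first listed main endpoint, and the objective is stated as a proportion in each group, so the absolute level matters as well as the contrast. The same proportions are reported at three interims, and Protocol 11 foresees public release of 3-year interim data. Part of any rise from interim to final would be produced by longer follow-up alone.

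The rule also cannot be programmed as written at an interim, where most women have no EOS. For dropouts, SAP 4.4.5 treats pain with a missing stop date as ongoing at end of study. Depending on whether that means her own exit or the planned study end, the same woman is a non-event or an event.

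**Working it through.** The documents give no expected chronic-pain rate, dropout rate, sample size or accrual period, so there is no planned figure to reproduce. Those inputs are assumed below, with ranges.

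**Inputs.** Window W = 182 days (SAP 6.4). Full follow-up L = 1826 days (60 months). Assumed: constant hazard h of pain that becomes chronic, and five-year cumulative incidence F of 5-30%, so h = -ln(1-F)/1826.

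**Share of follow-up that cannot be scored in a completer:** 182/1826 = 10.0%.

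**Exposure-adjusted rate as SAP 6.4.2 defines it, no dropout.** Per woman:

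- scored events E = 1 - exp(-h(L-W))
- risk time R = E/h + W·exp(-h(L-W))
- ratio to truth = (E/R)/h

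Example with F = 20%: h = 0.2231/1826 = 0.0001222 per day; h(L-W) = 0.0001222 × 1644 = 0.2009; E = 0.1820; R = 0.1820/0.0001222 + 182 × 0.8180 = 1489 + 149 = 1638 days; E/R = 0.0001111; ratio = 0.909. A true five-year incidence of 20% is scored as 18.2%.

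| Follow-up | F = 5% | 10% | 20% | 30% |
|---|---|---|---|---|
| 1826 days | 0.902 | 0.905 | 0.909 | 0.914 |
| 1096 days | 0.836 | 0.838 | 0.842 | 0.846 |
| 365 days | 0.502 | 0.503 | 0.504 | 0.506 |

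**With dropout (simulation, exponential dropout).** At F = 15% the ratio is 0.905 with no dropout, 0.892 with 30% and 0.869 with 50%. At F = 10-20%, with 10-50% dropout, it runs from 0.867 to 0.901. If 30% are also censored early but followed on, it is 0.881 to 0.918. The loss is slightly smaller because pain starting before those censoring dates can still reach 182 days.

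**Interims.** The unscorable share of risk time is mean(min(T, 6))/mean(T), with T in months since procedure and uniform accrual over an assumed 18 or 30 months:

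- End of enrolment: 5/9 = 56% (18 months), 5.4/15 = 36% (30 months). Between 6/30 = 20% and 6/18 = 33% of women have under 6 months.
- One year later: 6/21 = 29%, 6/27 = 22%.
- Three years later: 6/45 = 13%, 6/51 = 12%.

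**Kaplan-Meier.** Without dropout the curve is right to about day 1640 and then flat. With 50% dropout and F = 20% it reads 17.2% at day 1640 against a true 18.2%.

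**Between arms (F = 20% for the true ratio of 1.0).** With 30% dropout in both arms, a true rate ratio of 1.0 stays 1.00 and 1.5 stays 1.50. Dropout of 50% v 30% turns 1.0 into 0.976; 50% v 10% turns it into 0.967.

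**Where to trim.** Ending risk time 182 days before last observation gives a ratio of 1.000 analytically and 0.993-1.008 in simulation. Trimming 182 days before the censoring date behaves differently when pain leads to removal. With F = 15%, no dropout, and an assumed 20% of onsets followed by removal 30-182 days later with pain persisting, that trim gives 0.80 of the true rate, against 0.91 under the SAP as written and 1.00 when trimming from last observation.

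**The case against.** A reader might infer that the last 182 days of every woman's risk time are blind, including those before a censoring event. The documents do not support that. Duration is tied to the pain stop date or EOS, not to the censoring date, and SAP 4.3 keeps collecting data after censoring. Pain that starts 60 days before an Essure removal and lasts 200 days meets the definition. A woman with an event stops contributing time at onset. The SAP does not, however, say outright that duration after censoring counts: SAP 6.4.5 summarises to end of study or censoring date, and SAP 6.5.1 tabulates later adverse events separately.

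Other points on that side:

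- Onset dating is inferred. This stands, and is itself a gap.
- For completers, the proportion who met the 6-month definition by month 60 is counted correctly. This stands for that proportion. It does not rescue a rate that dates events at onset and counts time in which onset cannot qualify.
- For dropouts the direction could reverse if a missing stop date is read as ongoing to the planned study end. This stands, and is a reason to define EOS.
- All pelvic and abdominal pain, chronic or not, is tabulated under SAP 6.5.1, so late-onset pain is still visible. That is true, but it does not correct the main endpoint.
- The interims give proportions without statistical comparison. That limits the harm, but those proportions still depend on follow-up length.

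**Conclusion.** The concern holds for absolute rates. For women followed event-free to month 60, dropout or a cutoff, the exposure-adjusted chronic-pain rate is too low: about 9-10% in completers (five-year incidence 5-30% assumed), 11-13% with 30-50% dropout (assumed), and more at the interims. Absolute rates at the interims and the final analysis are therefore not comparable. These sizes rest on a constant hazard, onset dating, and EOS read as the woman's own exit.

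A reader might go on to infer a materially biased comparison between arms. The figures do not show one: the ratio is essentially unchanged with similar follow-up and moves to about 0.97 even at 50% v 10% dropout. Kaplan-Meier in completers is affected only in the last 182 days. Because the analysis is declared exploratory and the comparative effect is small, this is a worthwhile correction and not an essential one.

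**What to change.** For the chronic-pain endpoint only, in SAP 6.4 and 6.4.1 to 6.4.4, and at each interim:

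1. State that the event date is pain onset.
2. Define EOS as the woman's own last observation: the 60-month visit, dropout or last contact, or the interim data cutoff. Apply this also when the stop date is missing.
3. State that pain starting before a censoring event (removal, hysterectomy, second method, start of hormonal manipulation) is judged on its full observed duration, including time after that event.
4. End chronic-pain risk time at the earlier of the censoring date and 182 days before last observation. Do not trim 182 days before the censoring date: that would discard pain whose duration was observed, and would do so mainly in the arm where removal is possible. Take the denominator as women with more than 182 days of observation.
5. Report pain starting in the last 182 days of observation separately, as chronicity not assessable.

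The cost is one SAP paragraph, a programming change and slightly less risk time. No new data are needed. Proportions will still depend on length of follow-up, so interim and final figures should be compared on the rate or at a common time point.

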**Table 3 – Search list for bleeding and pain**

Category	SMQ definition
Abnormal uterine bleeding	Dysfunctional uterine bleeding; Genital hemorrhage; Genital haemorrhage; Menometrorrhagia; Menorrhagia; Metrorrhagia; Polymenorrhagia; Uterine hemorrhage; Uterine haemorrhage; Vaginal hemorrhage; Vaginal haemorrhage; Amenorrhea; Amenorrhoea; Hypomenorrhoea; Hypomenorrhoea; Oligomenorrhoea; Oligomenorrhoea; Bleeding anovulatory; Menstrual disorder; Menstruation delayed; Menstruation irregular.
Lower abdominal and/or pelvic pain	Abdominal pain; Abdominal pain lower; Abdominal tenderness; Abdominal discomfort; Incision site pain; Implant site pain; Medical device discomfort; Medical device pain; Medical device site discomfort; Medical device site pain; Suprapubic pain; Visceral pain; Post ablation tubal ligation syndrome; Pubic pain;; Back pain(excluding LLT upper back pain; including LLT lower back pain); Groin pain; Genito-pelvic pain/ penetration disorder; Uterine cervical pain; Ovulation pain; Pelvic pain; Pelvic discomfort; Dyspareunia; Adnexa uteri pain; Uterine tenderness; Uterine pain; Uterine spasm; Dysmenorrhoea; Menstrual discomfort; Premenstrual cramps;

For allergic/hypersensitive reactions and autoimmune disorders, final determination of whether or not a hypersensitivity/allergic event or autoimmune disorder event has occurred will be based on the determination of the adjudication committee.

For invasive gynecologic surgery, [Table 4](#) lists the terms from eCRF that will be considered as invasive gynecologic surgery.

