- In addition, any subject who experiences an AE of pelvic / lower abdominal pain in this study will be evaluated for possible hypersensitivity / allergic reaction including central laboratory evaluation and case adjudication (see below for further details on hypersensitivity / allergy).

Per the definition by the American College of Obstetricians and Gynecologists, chronic pelvic pain is pain in the pelvic area that lasts for 6 months or longer. In those subjects reporting lower abdominal / pelvic pain at any time during the study, either spontaneously or in response to the regularly scheduled PRO tool and who have been judged to have experienced an AE, it will be determined if duration of the pain meets this definition. The percentage of subjects in each group (laparoscopic and hysteroscopic) who are determined to have new onset or worsening chronic pelvic / lower abdominal pain will be reported. Additional analyses will be carried out looking at total number of pain reports (regardless of chronicity), intensity, and pain interference.

- **Bleeding:** The proportion of subjects reporting AEs of abnormal uterine bleeding (AUB) after insertion of Essure System compared to the proportion of subjects reporting AEs of AUB after laparoscopic tubal sterilization. Total incidence of new onset or worsening abnormal bleeding events will be based on AE reporting. If a potential bleeding AE is reported at a scheduled visit or if the subject spontaneously reports such an event to the site at some other time, the event will be evaluated per standard AE assessment. In the event of a report outside of a scheduled visit or scheduled PRO administration, the Aberdeen Menorrhagia Severity Scale (AMSS) and two intermenstrual bleeding questions will not be re-administered as the recall period for these PRO tools is 3 months and these data are captured during the scheduled PRO tool administration which occurs every 3 months.

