If during the course of a scheduled PRO administration (see [Table 9–2](#) and [Section 9.2.3.1](#)) the subject indicates that she has experienced abnormal bleeding that reaches a preset threshold on the AMSS, even if the subject has not spontaneously reported this event, the investigator will be alerted and instructed to investigate this finding in order to determine whether or not an AE has occurred. Standard criteria for AE assessment (e.g., new or worsening symptom) will be used and all investigators will be trained on standard AE assessment. The threshold for investigation of bleeding as an AE will be a total Aberdeen Scale score of ≥ 40 . Investigation will also be triggered by responses that meet a preset threshold on specified single questions, including those on the two intermenstrual bleeding questions. These are summarized in [Section 9.2.3.1](#). The percentage of subjects in each group (laparoscopic and hysteroscopic) who are determined to have an AE related to AUB will be reported. Not all reports of AUB reported on the PRO will be considered AEs. This is particularly notable in the case of a subject who has pre-existing AUB that continues to be unchanged post-sterilization procedure. Additional analyses will be carried out looking at duration and severity of abnormal bleeding, type of abnormality (e.g., menorrhagia, metrorrhagia), and subject impact based on the PRO tools.

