- Characteristics of subjects undergoing Essure Confirmation Test compared to subjects who do not comply with the requirement for Essure confirmation testing.

Statistical analyses will be explorative and descriptive in nature and no confirmatory hypothesis tests are intended to be performed; p-values will be interpreted as a metric for uncertainty. Therefore, no adjustment for multiplicity will be necessary.

All endpoints and variables will be analyzed by descriptive statistical methods. The number of data available and missing data, mean, standard deviation, minimum, lower and upper quartiles, median, and maximum will be calculated for continuous data. Frequency tables will be generated for categorical data. They will include the number of missing values as additional categories. Relative frequencies will be shown as percentages which will be calculated as a proportion including the category of missing values. Incidence rates and proportions will be used to summarize main endpoints and other variables. For time-to-event endpoints, hazard ratios derived from a Cox regression model, and Kaplan-Meier estimates will be provided.

If not specified otherwise, the analyses are presented in a way that events will be assigned to the treatment which was given initially at the index event.

The main analyses will be performed on a PS confounder-adjusted population of the Full Analysis Set in order to adjust for measured confounding as well as on the Full Analysis Set population. After all subjects have been enrolled, an outcome-blinded independent party, which only has access to the treatment variable and baseline variables, will perform the PS matching. All baseline variables will be considered for inclusion into the model; however, the following variables have shown previous evidence to likely be included in the model: age, race, BMI, US geographical region, insurance, hormonal contraception use at baseline, pre-existing pain disorders (pelvic pain, low back pain, chronic headache, fibromyalgia), disorders associated with hysterectomy (fibroids, ovarian pathology, endometriosis, prolapse, hyperplasia), gastrointestinal disorders (e.g., irritable bowel syndrome), pre-existing autoimmune disease, pre-existing diabetes, and pre-existing hypertension.

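### SAP Table 3 is broader than the protocol's pelvic pain endpoint and pools absent with heavy menses, and the SAP omits the protocol's etiology exclusion

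*SAP*

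**What the plan says.** SAP 6.4 says that, for the main outcomes, Table 3 "lists the SMQ search terms for abnormal uterine bleeding and lower abdominal and/or pelvic pain". For pain it adds a duration rule of more than 182 days, or ongoing at end of study with a start 182 days earlier.

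**Pain.** The row contains "Abdominal pain; Abdominal pain lower; Abdominal tenderness; Abdominal discomfort; Incision site pain; Implant site pain", then visceral pain among others, and "Back pain(excluding LLT upper back pain; including LLT lower back pain); Groin pain". Protocol 5.2.1 sets the endpoint as chronic lower abdominal and/or pelvic pain and states that "chronic pelvic pain is pain in the pelvic area that lasts for 6 months or longer". SAP 6.4 repeats that definition. Protocol 10.3, listing candidate propensity-score variables, names "pre-existing pain disorders (pelvic pain, low back pain, chronic headache, fibromyalgia" as separate items.

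**Bleeding.** The row contains "Amenorrhea; Amenorrhoea; Hypomenorrhoea; Hypomenorrhoea; Oligomenorrhoea; Oligomenorrhoea" and "Menstrual disorder; Menstruation delayed; Menstruation irregular", alongside menorrhagia, metrorrhagia and the haemorrhage terms. Protocol 5.2.1 gives no term list. It illustrates AUB only through a planned further analysis by "type of abnormality (e.g., menorrhagia, metrorrhagia".

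**Etiology.** For both endpoints, Protocol 10.3 says that adverse events with another apparent cause will be identified and removed in both groups. SAP 6.4 and Table 3 contain no such step.

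**The concern.** The search list in effect defines the endpoint. A programmer who follows the SAP would count a woman with seven months of low back pain as a case of chronic lower abdominal or pelvic pain. A woman whose reported event is amenorrhoea would count as a bleeding case. Nothing written in the SAP removes either event on grounds of cause.

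Two distortions are possible. Off-target events equally common in both arms pull ratio measures towards 1. Off-target events that differ by arm bias every measure, in whichever direction the difference runs. A difference is plausible. The protocol's pain screener (Section 17.1) asks only about the pelvis and lower abdomen, so back pain reaches the database by other reporting, and Protocol 5.2.1 itself expects outside influences to affect reporting differently in the two groups. Incision-site pain from the index procedure arises in the laparoscopic arm; pain at the Essure insert arises only in the Essure arm.

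**Working it through.** The documents state no sample size, power or event rates, so there is no planned figure to reproduce. The check compares the texts, then works an illustration on assumed rates.

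**1. What Table 3 contains.** The pain row has 29 terms. Six are not located in the pelvis or lower abdomen: abdominal pain (unspecified), abdominal tenderness, abdominal discomfort, visceral pain, incision-site pain, and back pain other than upper back pain. The bleeding row has 21 entries, or 15 distinct terms after merging spelling variants and repeats. Four of the 15 mean absent, scanty, infrequent or delayed menses: amenorrhoea, hypomenorrhoea, oligomenorrhoea and menstruation delayed.

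**2. What could remove such events.**
- The Protocol 10.3 exclusion is absent from the SAP. Version lag does not explain this: Section 10.3 is marked as last modified by Amendment 2, and the SAP lists Amendment 3 as its basis.
- Committee adjudication is assigned to allergic/hypersensitivity and autoimmune events (SAP 6.4, Protocol 14.3). Pelvic pain goes to the committee only to ask whether hypersensitivity played a part.
- SAP 6.8 varies the censoring rule only. No planned analysis varies the endpoint definition.

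**3. Shared off-target events (assumed rates).** Let true incidence be 6% laparoscopic and 12% Essure, and let off-target events occur independently with incidence b in both arms. Observed incidence is p' = 1 − (1 − p)(1 − b). The SAP's ratio measure is the hazard ratio. Under proportional hazards it equals ln(1 − p'E) / ln(1 − p'L), where L is laparoscopic and E is Essure.

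| b | p'L | p'E | Risk difference (points) | Risk ratio | Hazard ratio |
|---|---|---|---|---|---|
| 0 | 6.00% | 12.00% | 6.00 | 2.00 | 2.07 |
| 3% | 8.82% | 14.64% | 5.82 | 1.66 | 1.71 |
| 5% | 10.70% | 16.40% | 5.70 | 1.53 | 1.58 |
| 8% | 13.52% | 19.04% | 5.52 | 1.41 | 1.45 |

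For b = 5%: p'L = 1 − 0.94 × 0.95 = 0.107 and p'E = 1 − 0.88 × 0.95 = 0.164. The risk difference shrinks only by the factor (1 − b), while the ratios shrink much more. At b = 5%, women with off-target events alone make up 0.94 × 0.05 / 0.107 = 44% of laparoscopic cases.

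**4. Unequal off-target events (same 6% and 12%).**
- Off-target 5% laparoscopic, 8% Essure: 19.04 − 10.70 = 8.34 points, risk ratio 1.78.
- Off-target 8% laparoscopic, 5% Essure: 16.40 − 13.52 = 2.88 points, risk ratio 1.21.
- Incision-site pain beyond 182 days in the laparoscopic arm only, no other background: at 1%, p'L = 1 − 0.94 × 0.99 = 6.94%, difference 5.06 points, risk ratio 1.73. At 3%, p'L = 8.82%, difference 3.18 points, risk ratio 1.36. The 1% to 3% range has no basis in the documents, and 3% is half the assumed laparoscopic rate.

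**The case against.** The strongest reply is that the protocol leaves endpoint detail to the SAP, so a broad list is the sponsor's to choose, and that the list is less broad than it first looks. Much of this stands.

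- Table 3 has no upper-abdominal term and excludes upper back pain. It does not count any abdominal or any back pain; the issue is the unspecified and non-pelvic terms.
- The endpoint is abnormal uterine bleeding, the protocol's examples are only examples, and its menstrual questionnaire asks about regularity and long cycles (although those items trigger no alert). A reader might infer that the bleeding row contradicts the protocol; the documents do not support that.
- A reader might infer that women amenorrhoeic on bridging hormones simply become bleeding events in the Essure arm. SAP 6.1.3 partly answers this: it censors at the start of hormonal manipulation and restricts the risk period in both groups for some bleeding analyses, without saying which. Endometrial ablation, however, is not a censoring event.
- Incision-site pain must last more than 182 days, so its contribution is probably small, and it is a real harm of the comparator. Dropping it from the main endpoint while keeping device-site pain would tilt the comparison.
- SAP 6.5.1 tabulates adverse events by preferred term, and bleeding and pelvic/abdominal pain as reported by the investigator. Components are therefore visible, but these tables do not give a narrow chronic pain incidence, risk difference or hazard ratio.

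SAP 6.2 might be read as supplying the missing exclusion, since it drops events that adjudication does not validate. The committee's written remit does not extend to the cause of pain or bleeding generally.

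**Conclusion.** The point holds in a limited form. The pain list is broader than the definition that both documents give, the bleeding list pools opposite phenomena, and a protocol step that would have limited both problems is missing from the SAP. The missing etiology exclusion is the clearest discrepancy between the two documents.

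A reader might go further and conclude that the endpoints are diluted and that device harm is hidden. The documents do not show this. They give no rates. With equal background the planned risk difference barely moves (6.0 to between 5.8 and 5.5 points), although the hazard ratio would fall from 2.07 to between 1.71 and 1.45. With unequal background the contrast can rise or fall. All these figures rest on assumed incidences, independence of on-target and off-target events and, for the hazard ratio, proportional hazards. Nor do the documents require replacing the main endpoint. What they support is reconciling the texts and showing how far the result depends on the list. This should be settled before the final analysis.

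**What to change.** 1. Carry the Protocol 10.3 etiology exclusion into SAP 6.4 for pain and AUB. State who decides and on what information, apply it without knowledge of group where possible, and list the excluded events by arm.
2. Pre-specify a narrow-list pain analysis, restricted to pelvic and lower-abdominal terms, beside the broad list for incidence, risk difference and hazard ratio. Treat arm-specific terms (incision-site pain, and implant or device pain) symmetrically, and show them separately.
3. Report AUB in two parts: heavy, intermenstrual or irregular bleeding, and absent, scanty, infrequent or delayed menses. Assign the non-specific menstrual disorder term to one part in advance.
4. Date the change, and say whether interim results by term and group had already been seen.

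The cost is an edit to the SAP text and Table 3 and one extra set of tables, with no new data collection. The drawback is that some true pelvic pain coded only as abdominal pain drops out of the narrow list, which is why both lists should be shown.
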